12.1.3 Schedule of procedures (Part C)

	Screening ¹	Treatment session						Follow-up ²			
		Day -1	Day 1	Days 2-6	Day 7	Days 8-13	Day 14	Day 15	Day 16	Day 17	Day 24 ±2
Informed consent	X										
Demography	X	X									
Medical history	X										
Inclusion/exclusion criteria	X	X									
Height and weight ³	X	X									
Dose of BEN8744 or placebo ⁴			X		X		X		X		
Inpatient visit ⁵											
Outpatient visit	X										
Safety assessments											
Physical examination ⁶	X	X	X	X		X		X		X	X
Laboratory safety tests ⁷	X	X	X	X		X		X		X	X
Serology	X										
Urine drug screen, and alcohol and cotinine tests	X	X	X								
Vital signs ⁸	X	X	X	X		X		X		X	X
12-lead safety ECG ⁹	X	X	X	X		X		X		X	X
Pregnancy/FSH test ¹⁰	X	X	X								
OAAS/S and VAS ¹¹			X		X ¹¹						
C-SSRS	X										
PK assessments											
Blood sampling ¹²											
Urine collection ¹³						X ¹³					
Ongoing subject review											
Concomitant medicines											
Adverse events											

Abbreviations: C-SSRS=Columbia-Suicide Severity Rating Scale; ECG = electrocardiogram; FSH = follicle stimulating hormone; FU = follow-up; OAAS = Observer's Assessment of Alertness/Sedation scale; PK = pharmacokinetics; VAS = visual analogue scale.

Notes:

1. Screening will be within 28 days before first dose.

2. Follow up will be 7 (± 2) days after discharge.
3. Height at screening only.
4. Subjects will receive a daily dose of BEN8744 or placebo, by mouth, on Day 1–14. Doses will be given at approximately the same time/s each day (± 15 min from time/s on Day 1). Doses will be taken once or twice daily in the fasted state, unless emerging data indicate they should be taken in the fed state. If BEN8744 will be given twice daily, the last dose will be given in the morning of Day 14.
5. Subjects will be resident on the ward from 1 day before their dose (Day –1) until up to 72 h after final dosing (Day 17).
6. Full physical examinations will be done at screening. Brief (symptom-directed) physical examinations will be done at all other timepoints. On Days 1, 7 and 14, the brief physical examinations should be done before dosing.
7. Laboratory safety tests consist of clinical chemistry, haematology and urinalysis.
8. Vital signs consist of: supine systolic and diastolic blood pressure, pulse rate, tympanic temperature and respiratory rate. During the period of residence, they will be assessed at the following timepoints on Days 1 and 14: predose, 2, 4, 8 and 12 h postdose. Predose vital signs (including on Days 2–13) should be measured up to 90 min before dosing. If twice-daily dosing, vital signs should be measured before the morning dose only.
9. Triplicate measurements (obtained ≥ 2 min apart) will be made at screening. Single measurements will be made at all other timepoints. Measurements should be made with subjects in a supine position, after resting for 5 min.
10. During the period of residence, ECGs will be recorded at the following timepoints on Days 1 and 14: predose, 2, 4, 8 and 12 h postdose. Predose ECGs (including on Days 2–13) should be done up to 2 h before dosing. If twice-daily dosing, ECGs should be done before the morning dose only.
11. Triplicate ECG recordings (made ≥ 2 min apart) will be made at screening; single recordings will be done at all other timepoints. Recordings should be made with subjects in a supine position, after resting for 5 min.
12. Once-daily dosing: Days 1 and 14 at predose and postdose at 0.25, 0.5, 1, 2, 3, 4, 6, 8, and 12 h; on Days 2 (24 h) and Day 15 (24 and 36 h); on Day 16 (48 h); and on Day 17 (72 h). Trough samples will be taken predose on Days 3, 5, 7, 9, 11, and 13.
13. Twice-daily dosing: Day 1 and 14 at predose, and postdose at 0.25, 0.5, 1, 2, 3, 4, 6, 8, and 12 h (pre-evening dose on Day 1); on Day 1 at 12.5, 13, 14, 15, and 16 h; Days 2 (20 and 24 h) and Day 15 (24 and 36 h); on Day 16 (48 h); and on Day 17 (72 h). Trough samples will be taken pre-morning dose on Days 3, 5, 7, 9, 11, and 13.
14. Blood samples for assay of BEN8744 will be taken on:

 - Once-daily dosing: Days 1 and 14 at predose and postdose at 0.25, 0.5, 1, 2, 3, 4, 6, 8, and 12 h; on Days 2 (24 h) and Day 15 (24 and 36 h); on Day 16 (48 h); and on Day 17 (72 h).
 - Twice-daily dosing: Day 1 and 14 at predose, and postdose at 0.25, 0.5, 1, 2, 3, 4, 6, 8, and 12 h (pre-evening dose on Day 1); on Day 1 at 12.5, 13, 14, 15, and 16 h; Days 2 (20 and 24 h) and Day 15 (24 and 36 h); on Day 16 (48 h); and on Day 17 (72 h). Trough samples will be taken pre-morning dose on Days 3, 5, 7, 9, 11, and 13.

15. Depending on the results of Part B, continuous urine collection for assay of BEN8744 may be taken after dosing on Day 1 and Day 14 at 0–12 h, 12–24 h, and on Day 2 and 15 (24–48 h), and Day 3 and 16 (48–72 h). A spot sample will be taken before dosing on Day 1 and 14.

When more than one procedure is scheduled at a specific timepoint, procedures should be done in the following order: ECG, vital signs, blood samples (at the scheduled time). Blood sampling should be done on time. Other procedures should be done as close as possible to the scheduled timepoint.

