2.7.1 Safety and tolerability

Laboratory assessments (routine haematology, clinical chemistry, and urinalysis), physical examinations, 12-lead ECGs, and vital signs (blood pressure, pulse rate, respiratory rate, and tympanic temperature) and C-SSRS (in Part C) will be done during dosing and frequently until the subject's last visit. Cardiac telemetry (Part A only) will be done from 1 h before until 24 h after dosing. The OAAS/S and VAS will be done frequently at specific timepoints immediately before PK blood samples, up to 72 h after dosing in Parts A and B, and up to 72 h after dosing on Day 1 in Part C, to monitor sedation. AEs will be recorded from time of consent until the subject's last visit.

2.7.2 *Pharmacokinetics*

Blood samples for assay of BEN8744 will be taken before, and frequently up to 72 h after dosing in Parts A and B, and up to 72 h after dosing on Day 1 and Day 14 in Part C.

Urine will be collected continuously for up to 72 h after dosing in Part B, and may be collected for up to 72 h after dosing on Days 1 and 14 in Part C, for assay of BEN8744 and its metabolites.

A predose faecal sample will be collected from Day -2 to predose on Day 1 in Part B Session 1. Faecal samples will be collected continuously for up to 72 h after dosing in Part B for the exploratory characterisation of BEN8744 and its metabolites.

3 **Contents**

Version control history	2
Protocol amendment summary	2
1 Signatures	5
2 Summary	6
2.1 Trial medication	6
2.2 Objectives	6
2.2.1 Primary objectives	6
2.2.2 Secondary objectives	6
2.2.3 Exploratory objectives	6
2.3 Endpoints	7
2.3.1 Primary endpoints	7
2.3.2 Secondary endpoints	7
2.3.3 Exploratory endpoints	7
2.4 Type of trial	7
2.5 Trial population	8
2.6 Trial design and methods	8
2.6.1 Part A	8
2.6.2 Part B	9
2.6.3 Part C	10
2.7 Assessments	10
2.7.1 Safety and tolerability	10
2.7.2 Pharmacokinetics	11
3 Contents	12
3.1 Table of Figures	15
3.2 Table of Tables	15
4 List of abbreviations	17
5 Trial personnel	21
6 Introduction	22
6.1 Background	22
6.2 Review of investigational medicinal product	23
6.2.1 Non-clinical pharmacology	23
6.2.2 Non-clinical pharmacokinetics	23
6.2.3 Non-clinical safety and toxicology	24
6.2.4 Clinical experience	26
6.3 Rationale for the trial	29
6.4 Participant input into trial design	29
6.5 Rationale for choice of dose(s)	29
6.5.1 Doses up to Cohort A4	30
6.5.2 Subsequent dose levels	32

6.6	Assessment and management of risk	33
6.7	Conducting the trial during the COVID-19 pandemic	36

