7.2.3 Exploratory endpoints

PK (Part B and optional in Part C): Ae_{72} , $f_e \cdot F$, CL_R

8 Overall trial design

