10.6 Selection and timing of dose for each subject

The treatments to be administered and intervals between subjects are described in sections 8.1 and 10.1. Subjects will be randomly assigned to treatment, as described in section 10.5 above.

Because BEN8744 has never been given to humans before, in Part A each new ascending dose will be staggered as described in section 10.5.

In Part C, doses will be given at the same time each day (if once daily dosing) or every 12 h at the same time each day (if twice daily dosing). Doses will be given ± 15 mins from times on Day 1.

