Table 10: Acceptable deviation times for Part C

Procedure	Study day	Timepoint	Acceptable deviation
PK blood sampling	Days 1 and 14	Predose (morning dose)	Up to 30 min before dosing
		Up to and including 1 h after the morning dose	± 5 min of the scheduled time
		After 1 h to 4 h after the morning dose	± 10 min of the scheduled time
		After 4 h to 24 h after the morning dose	± 15 min of the scheduled time
	Days 2–13	Predose (morning dose)	Up to 30 min before dosing
	Day 15–17	> 24 h after the morning dose	± 1 h of the scheduled time
	Day 18 onward	Outpatient visits	± 2 days
PK urine and faecal sample collection (optional)	Days 1–3 and 14–16	Any timepoint (except predose urine spot sample)	± 90 min of the scheduled time
All other procedures*	Days 1 and 14	Predose (morning dose)	Up to 90 min before dosing*
		Up to and including 4 h after the morning dose	± 10 min of the scheduled time
		After 4 h to 24 h after the morning dose	± 15 min of the scheduled time
	Days 2–13	Predose (morning dose)	Before dosing
	Day 15–17	> 24 h after the morning dose	± 1 h of the scheduled time
	Day 18 onward	Outpatient visits	± 2 days

* Samples for urinalysis may be collected anytime from when the subject awakes until the scheduled time.

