16.1.2 Urine sample parameters (Parts B and C)

Text	Symbol	Definition	Calculation
Urinary recovery			
Ae ₇₂		Cumulative amount of unchanged drug excreted into the urine at 72 h	Calculated as the sum of the products of concentration and urine volume over the appropriate collection intervals
Renal clearance			
CL _R		Renal clearance of drug from plasma	Calculated from the ratio of the appropriate values for urinary recovery and area under the plasma concentration–time curve, using the following formula:
			$CL_R = \frac{Ae_{24}}{AUC_{24}}$

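### Part C Day 1 Ae72 spans about 3 doses (once daily) or 6 (twice daily), so it is not comparable with Day 14 or Part B Ae72, and fe·F has no stated divisor

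*Combined protocol and SAP*

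**What the plan says.** **Collection.** The urine note to the Part C schedule (12.1.3) says that continuous collection "may be taken after dosing on Day 1 and Day 14 at 0–12 h, 12–24 h, and on Day 2 and 15 (24–48 h"), and then on "Day 3 and 16 (48–72 h"). Section 2.7.2 agrees: urine "may be collected for up to 72 h after dosing on Days 1 and 14 in Part C". So does Table 10 in section 12.2, which gives the collection days as "Days 1–3 and 14–16". The 72 h window after Day 1 is therefore intended and not a slip in one note.

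**Dosing.** Section 12.1.3 also states: "Subjects will receive a daily dose of BEN8744 or placebo, by mouth, on Day 1–14". Under a twice-daily regimen, section 10.6 has doses "every 12 h at the same time each day (if twice daily dosing"). No dose is held on Days 2 or 3. In twice-daily groups the last dose is on the morning of Day 14.

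**Parameters.** Section 7.2.3 lists Ae72, fe·F and CL_R under "PK (Part B and optional in Part C"). Section 16.1.2 defines Ae72, for both parts, as "Cumulative amount of unchanged drug excreted into the urine at 72 h", computed as the sum of concentration times volume over the collection intervals. It has no separate rule for multiple dosing and no formula for fe·F, which is defined only in the abbreviations list as a fraction of the administered drug. CL_R is Ae24/AUC24. The Part C plasma lists (7.2.2 and 16.1.1) contain AUCtau but not AUC24.

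**The concern.** Ae72 is a natural recovery measure after a single dose, as in Part B. Carried unchanged into Part C, it covers different numbers of doses on the two collection days. After Day 1 the window includes the doses of Days 2 and 3; after Day 14 no further dose falls in it.

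A table of Ae72 by day, or of Part B beside Part C, would then show a large difference that comes from dose counting. A reader could take it for time-dependent renal excretion, which is a question that a Day 1 versus Day 14 comparison is meant to answer. The missing fe·F divisor adds to this, because the analyst must choose it and the choice changes the twice-daily Day 1 result by up to 6-fold.

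**Working it through.** The plan gives no Ae72 or fe·F value, so there is no figure to reproduce.

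**Inputs**
- Window: 0–72 h after the Day 1 dose and after the Day 14 dose (12.1.3).
- Dose times within the Day 1 window: 0, 24, 48 h (once daily) or 0, 12, 24, 36, 48, 60 h (twice daily) (10.6, 12.1.3).
- Half-life h: about 2–4 h (6.2.4, repeated in 6.5.2).
- Assumptions: linear PK, with the same bioavailability and renal fraction for every dose.

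**Day 1.** In units of one dose's eventual urinary amount, a dose given at time t has contributed 1 − 2^(−(72−t)/h) by 72 h. Summing over doses:
- Once daily, h = 4: 3 − (2^−18 + 2^−12 + 2^−6) = 2.98. At h = 2: 3.00.
- Twice daily, h = 4: 6 − (2^−18 + 2^−15 + 2^−12 + 2^−9 + 2^−6 + 2^−3) = 6 − 0.143 = 5.86. At h = 2: 5.98.

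**Day 14.** One dose plus carry-over from earlier doses, approximately 1/(1 − 2^(−tau/h)):
- Once daily: 1.00 (h = 2) to 1/(1 − 2^−6) = 1.02 (h = 4).
- Twice daily: 1.02 (h = 2) to 1/(1 − 2^−3) = 1.14 (h = 4).

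| | Once daily, h = 2 | Once daily, h = 4 | Twice daily, h = 2 | Twice daily, h = 4 |
|---|---|---|---|---|
| Doses in Day 1 window | 3 | 3 | 6 | 6 |
| Day 1 Ae72 | 3.00 | 2.98 | 5.98 | 5.86 |
| Day 14 Ae72 | 1.00 | 1.02 | 1.02 | 1.14 |
| Day 1 / Day 14 | 3.0 | 2.9 | 5.9 | 5.1 |

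**Sensitivity.** With first-order absorption (ka = 1.5/h, an assumption) and h = 4, twice-daily Day 1 becomes 5.84 and Day 14 becomes 1.16, a ratio of 5.0. At assumed half-lives of 6–8 h, Day 1 Ae72 is 2.86–2.93 (once daily) or 5.43–5.67 (twice daily).

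**fe·F from Day 1 Ae72, relative to the single-dose value, by divisor** (h = 2–4, with and without absorption)

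| Divisor | Once daily | Twice daily |
|---|---|---|
| One administered dose | 2.98–3.00 | 5.84–5.98 |
| Daily dose | 2.98–3.00 | 2.92–2.99 |
| Cumulative dose in the window | 0.99–1.00 | 0.97–1.00 |

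**Recovery over the dosing interval instead.** On Day 1 the amount over the first interval is 1 − 2^(−tau/h). Once daily (0–24 h) this gives 98–100% of one dose's urinary amount. Twice daily (0–12 h) it gives 1 − 2^−3 = 88% to 1 − 2^−6 = 98%, or 86–98% when absorption is allowed for. On Day 14 the contributions of successive doses telescope to 1 − 2^(−n·tau/h), where n is the number of doses given; this is 1.00 for either regimen.

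**The case against.** - **Ae72 is correct as defined.** It is a cumulative amount, and the plan nowhere says that it is to be read as the recovery of one dose. This stands as far as it goes. But the plan uses one name and one formula for windows holding six (or three) doses and one dose, and nothing warns the reader.
- **A reader might infer that fe·F will be 3 or 6 times too high.** The documents do not support that. There is no fe·F formula, and the abbreviation, read literally, fits the cumulative dose as divisor, which leaves no material error. The 3- or 6-fold error needs a single-dose divisor. That would match how Dose has to be read in CLss/F = Dose/AUCtau, but it is not stated for fe·F.
- **A reader might infer that CL_R is distorted.** It is not materially so. Ae24 and AUC24 cover the same 24 h. Once daily, AUC24 is AUCtau; twice daily, Day 1 blood sampling continues through the second interval to 24 h. The absence of AUC24 from the Part C list is a listing gap.
- **A reader might infer that the later urine is wasted.** That goes too far. The fractions are separate, so the 0–12 h and 0–24 h amounts can be computed from what is already planned, and the 24–72 h fractions could serve metabolite work (7.1.3). They cannot support CL_R on Day 1, because the scheduled blood samples after 24 h are troughs.
- **The multiples assume linearity.** Section 6.2.4 reports greater than proportional exposure and high between-subject variation, and section 11 places evening doses after dinner. The dose count is certain; the decimals are not.
- **Little depends on it.** Part C urine is optional, depends on significant parent drug being found in Part B urine, and would be limited to two dose levels. This is accepted, and it sets the severity.

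**Conclusion.** The point holds for Ae72. Followed exactly, the plan gives a Day 1 Ae72 in Part C of about 3 (once daily) or 6 (twice daily) single-dose recoveries, against about 1.0–1.2 after Day 14 and one in Part B. The apparent fall from Day 1 to Day 14 would be about 3-fold or 5- to 6-fold with unchanged renal excretion. The twice-daily case matters more, since section 6.2.4 expects that regimen in Part C. These sizes rest on linear PK, equal bioavailability across doses and a half-life of 2–4 h.

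For fe·F the finding is that the divisor is undefined. The consequence on Day 1 ranges from none (cumulative dose), through about 3-fold (daily dose), to 3- or 6-fold (one dose). Part B is unaffected, and Day 14 and CL_R are not materially distorted. The endpoint is exploratory and optional, so severity is low.

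**What to change.** For Part C:
- Replace Ae72 with recovery over the dosing interval, Ae_tau, on Days 1 and 14: 0–24 h once daily, 0–12 h twice daily. The planned fractions already split at 12 and 24 h.
- Set fe·F = Ae_tau / dose per interval, and CL_R = Ae_tau / AUC_tau, using the interval AUC already listed for Part C.
- Keep Ae72 for Part B.
- Let the Day 1 collection end once the interval is covered, unless the 24–72 h fractions are wanted for metabolites; if so, say so.

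**Cost.** This is a wording change in sections 2.3.3, 2.7.2, 7.2.3, 12 (pharmacokinetics text), 12.1.3, 12.2 (Table 10) and 16.1.2. The derivations can be carried into the statistical analysis plan that section 16.2.1 says is still to be prepared. It could spare participants up to 48 h of urine collection once daily, or up to 60 h twice daily if collection stops at 12 h.

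**Downside.** With twice-daily dosing, Day 1 Ae_tau captures about 86–98% of one dose's urinary amount, so it will sit slightly below Part B Ae72. Under linear PK, Day 14 Ae_tau does not have this shortfall and is the better value to set beside Part B.

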12.2 Sampling timepoints and additional tests

With the sponsor's approval, additional timepoints may be introduced, and changes to timepoints may be made, if we have reason to believe that the change might improve the quality of the data (for example, if we believe that an important effect of the IMP is occurring at a time when no measurements are scheduled), or if extra procedures are needed in the interest of subject safety. However, the total volume of blood taken in the trial will not exceed the value given in section 12.5. Any additional urine collections may include continuous, total collections, if necessary. Any additional faecal collections may include continuous, total collections, if necessary. An additional 48 hours' residence in the ward (including in each treatment period in Part B), and additional outpatient visits, will be permitted, in the event of a technical failure, and/or if extra observations or samples of blood or urine are needed.

Extra procedures and changes to timepoints which have a significant impact on the scientific value and/or safety of the trial participants will be implemented only after approval of a substantial amendment from the Regulatory Authority (MHRA), unless the changes constitute an urgent safety measure.

With the sponsor's approval, the washout period between treatments in Part B may be changed, if data collected during the trial support the change. However, the washout period will not be reduced to less than 5 half-lives of the trial medicine.

The following will **not** be regarded as protocol deviations.

Table 9: Acceptable deviation times for Parts A and B

Procedure	Timepoint	Acceptable deviation
PK blood sampling	Predose	Up to 30 min before dosing
	Up to and including 1 h postdose	± 5 min of the scheduled time
	After 1 h to 4 h postdose	± 10 min of the scheduled time
	After 4 h to 24 h postdose	± 15 min of the scheduled time
	More than 24 h postdose	± 1 h of the scheduled time
PK urine and faecal sample collection (Part B only)	Any timepoint (except predose urine spot sample and faecal sample)	± 90 min of the scheduled time
All other procedures*	Predose	Up to 90 min before dosing
	Up to and including 4 h postdose	± 10 min of the scheduled time
	After 4 h to 24 h postdose	± 15 min of the scheduled time
	More than 24 h postdose	± 1 h of the scheduled time

* samples for urinalysis may be collected anytime from when the subject awakes until the scheduled time.

Table 10: Acceptable deviation times for Part C

Procedure	Study day	Timepoint	Acceptable deviation
PK blood sampling	Days 1 and 14	Predose (morning dose)	Up to 30 min before dosing
		Up to and including 1 h after the morning dose	± 5 min of the scheduled time
		After 1 h to 4 h after the morning dose	± 10 min of the scheduled time
		After 4 h to 24 h after the morning dose	± 15 min of the scheduled time
	Days 2–13	Predose (morning dose)	Up to 30 min before dosing
	Day 15–17	> 24 h after the morning dose	± 1 h of the scheduled time
	Day 18 onward	Outpatient visits	± 2 days
PK urine and faecal sample collection (optional)	Days 1–3 and 14–16	Any timepoint (except predose urine spot sample)	± 90 min of the scheduled time
All other procedures*	Days 1 and 14	Predose (morning dose)	Up to 90 min before dosing*
		Up to and including 4 h after the morning dose	± 10 min of the scheduled time
		After 4 h to 24 h after the morning dose	± 15 min of the scheduled time
	Days 2–13	Predose (morning dose)	Before dosing
	Day 15–17	> 24 h after the morning dose	± 1 h of the scheduled time
	Day 18 onward	Outpatient visits	± 2 days

* Samples for urinalysis may be collected anytime from when the subject awakes until the scheduled time.

12.3 Follow-up

Subjects will return to the ward 7 ± 2 days after dosing (Part A) or after their final dose of trial medication (Parts B and C) for a follow-up visit. Withdrawn subjects who consent to a follow-up visit will undergo the same procedures (see section 9.4).

The follow-up period may be extended if:

1. a subject has an unresolved AE at the follow-up visit, which, in the opinion of the investigator, merits further follow-up;

2. plasma concentrations of IMP were higher than predicted, and/or the half-life of the IMP was very long, and the investigator considers that additional follow-up is necessary; or
3. new information becomes available that supports an extended follow-up period.

The investigator will decide on the nature of the follow-up. For example, subjects may have a telephone follow-up at which they are asked about AEs, or subjects may be asked to attend extra outpatient visits for additional monitoring of blood levels or effects of IMP, and for extra safety tests. The extra safety tests might include tests that are not described in this protocol. The investigator reserves the right, during or after the study, to repeat safety tests or to do any extra safety tests that are in the best interest of the subjects.

12.4 Methods

Blood collection

Blood will be taken by venepuncture or via a cannula. Cannulae may be inserted under local anaesthesia with lidocaine 0.5%, for withdrawal of venous blood.

After each blood sample, the cannula will be flushed with 3–5 mL normal saline, to keep it patent. In order to minimise dilution of each subsequent blood sample with normal saline, the following procedure will be used: about 1 mL will be drawn via the cannula into the sampling syringe, and discarded. The definitive blood sample will then be taken.

Blood volumes of specific types of samples may vary from those described below, but any change to the sample volumes will not cause the total volume of blood taken during the study to exceed that given in section 12.5.

Samples for laboratory safety tests

Blood will be taken for:

- haematology (2.7 mL in EDTA)
- clinical chemistry, serology, serum pregnancy and/or FSH (4.0 mL in tubes with a gelatin plug)

Blood samples will be collected into 13 × 75 mm tubes. Urine and faeces will be collected in Universal containers. Samples will then be transferred to the laboratory. For logistical reasons, blood, urine, and/or faecal samples may be collected in tubes other than those stated above.

Processing and analysis of samples for laboratory safety tests

Processing of samples will be done by the HMR Analytical Laboratory in accordance with the laboratory's SOPs.

The HMR Analytical Laboratory will do safety tests on blood and urine samples using instruments interfaced to a validated laboratory information management

system (LIMS). Data from analysers that are not interfaced will be entered manually into the LIMS.

Table 11: Laboratory safety tests

Haematology:	Clinical chemistry:
• haemoglobin (Hb)	• urea
• red blood cells (RBC)	• creatinine
• mean corpuscular volume (MCV)	• uric acid
• mean corpuscular haemoglobin (MCH)	• total bilirubin
• mean corpuscular haemoglobin concentration (MCHC)	• total protein
• haematocrit	• albumin
• white blood cells (WBC) and differential (neutrophils, lymphocytes, monocytes, eosinophils, basophils)	• globulin
• platelets	• alkaline phosphatase (ALP)
	• aspartate aminotransferase (AST)
	• alanine aminotransferase (ALT)
	• gamma-glutamyl transpeptidase (GGT)
Urinalysis:	• glucose
• dipstick: protein, blood, ketones, glucose, bilirubin, urobilinogen, leukocyte esterase, specific gravity, nitrites, pH	• phosphate
• microscopy: only if dipstick test for protein, blood, leukocyte esterase or nitrites is abnormal	• cholesterol
	• triglycerides
	• potassium
	• sodium
	• calcium
	• chloride
Serology:	
• hepatitis B (hepatitis B surface antigen)	
• hepatitis C antibody	
• HIV screen (HIV 1 and 2)	

Pregnancy and FSH tests

Serum pregnancy and serum FSH tests will be done using an immunochemiluminometric method.

Drugs of abuse, alcohol, and cotinine tests

Urine will be tested for drugs of abuse, alcohol, and cotinine according to the laboratory's SOP. Tests will include: amphetamines, cocaine, opiates, cannabis, barbiturates, benzodiazepines, alcohol, and cotinine.

Collection and processing of samples for pharmacokinetic analysis

Details on blood, urine, and faecal sample collection and processing, including labelling and shipment instructions, will be documented in a separate study procedures manual.

Physical examination

Physical examination will be done by a physician. The following will be examined: general appearance; head, ears, eyes, nose and throat; thyroid; lymph nodes; back and neck; heart; chest; lungs; abdomen; skin; and extremities. The following systems will be assessed: musculoskeletal and neurological.

Height and weight

Height and weight will be measured by trained staff at HMR.

Vital signs

Blood pressure and pulse rate will be measured using SpaceLabs oscillometric equipment. Measurements will be made with subjects in a supine position; subjects will remain supine for at least 5 min before vital signs are measured.

Tympanic temperature will be measured using digital thermometers.

Respiratory rate will be measured by observation of the chest.

Repeat vital signs measurements

During the trial, if vital signs fall outside the ranges in Table 12, a physician will review and decide on an appropriate course of action. The procedure will be repeated only if instructed by a physician.

Table 12: Vital signs ranges

Vital sign	Range
Supine systolic blood pressure	90–140 mm Hg
Supine diastolic blood pressure	40–90 mm Hg
Supine pulse rate	40–100 beats/min
Temperature	35.5–37.8°C
Respiration rate	10–16 breaths/min

If the result of the repeat measurement is still out of range, the investigator will decide on an appropriate course of action.

Standard 12-lead ECGs

12-lead ECGs will be recorded using Mortara ELI250c and ELI280 cardiographs. Each recording will be printed on a single A4 page at paper speed 25 mm/sec and

calibrated to 10 mm/mV. Recordings will be made with subjects in a supine position; subjects will remain supine for at least 5 min before the ECG is recorded. PR, RR, QRS and QT intervals will be captured on source documents. QT interval will be corrected using Fridericia's formula (QTcF).

During the trial, if ECG values fall outside the ranges in Table 13, a physician will review and decide on an appropriate course of action. The procedure will be repeated only if instructed by a physician.

Table 13: ECG ranges

ECG parameter	Range
Ventricular rate	35–100 beats/min
QRS	≤ 120 msec
PR interval	110–220 msec
QTcF (men)	≤ 450 msec
QTcF (women)	≤ 470 msec

If the result of the repeat measurement is still out of range, the investigator will decide on an appropriate course of action.

Holter monitoring (Part A only)

24-h Holter monitoring will be done at screening using recorders made either by Ela Medical or Burdick. The results will not be recorded in detail in the CRF unless they constitute an AE.

Telemetry (Part A only)

Heart rhythm will be monitored continuously (telemetry, 3-lead ECG) from 1 h before until 24 h after dosing, using a SpaceLabs system. Results from that safety monitoring will be recorded in detail in the CRF only if they constitute an AE.

Observer's Assessment of Alertness and visual analogue scales

Symptoms of sedation will be assessed using OAAS/S and VAS.

In the OAAS/S, the investigator or their delegate will score the subject's level of alertness on a scale of 0 to 5, where 0 is absence of response to stimulus, and 5 is readily responsive to the subject's name in a normal tone.

In the VAS, subjects will complete a self-reported post-dosing questionnaire. Subjects will be asked to score/rate their alertness. To reduce variability, subjects will be able to see their previous responses. A copy of the questionnaire can be found in Appendix A.

Columbia-Suicide Severity Rating Scale (C-SSRS)

The C-SSRS is a suicidal ideation rating scale used to evaluate suicidality³⁵. The questionnaire will be administered by the investigator or their delegate. The 'baseline' questionnaire will be used at screening, and the 'since last visit' questionnaire will be used at all other timepoints.

